ACTH is FDA-approved for treatment of MS relapses, infantile spasms, and multiple non-neurologic disorders. ACTH has both corticotropic and neurotropic properties (14), and has the potential to benefit both the inflammatory and neurodegenerative aspects of MS, respectively. Because of its corticotropic properties, long term use may result in steroid-related adverse effects (AE's). Administration of steroids as a pulsed regimen has been generally found to be well tolerated with few of the usual AEs associated with chronic corticosteroid use (12), although reduction in bone mineral density has been reported (15). The multiple mechanisms of ACTH action may offer advantages over steroids alone for the treatment of MS. Any slowing of progression resulting from treatment of progressive forms of MS with ACTH could be due to its corticotropic effects, its neuroprotective effects, and/or corticosteroid-independent effects on the immune response (16). A recent preliminary report evaluating pulsed ACTH versus pulsed MP as an add-on to interferons for treatment of RRMS found a significant benefit of pulsed ACTH (compared to pulsed MP) in reducing relapses over one year (17).

3. Hypotheses

1. ACTH administered as a monthly pulse (consisting of three consecutive days of subcutaneous injection) will be safe and well-tolerated in progressive MS patients.
2. Pulsed ACTH treatment will slow the progression of sustained physical disability of ambulation, as measured walking speed (T25FW), walking endurance (6 minute walk test, 6MWT), the Hauser ambulation index (AI), and the MS walking scale (MSWS-12), all validated measures related to ambulation in MS patients.
3. Pulsed ACTH treatment will slow the progression of sustained cognitive disability as measured by the Brief Repeatable Battery of Neuropsychological Tests (BRB-N), a measure of cognitive impairment that has been specifically validated for MS.
4. Pulsed ACTH treatment will reduce the proportion of subjects who show a sustained progression of the EDSS over the course of the study. (EDSS is a validated measure of overall MS disability).
5. Pulsed ACTH will reduce the decline in retinal nerve fiber layer thickness as measured by optical coherence tomography (OCT).

4. Inclusion and Exclusion Criteria

1. Inclusion criteria:
 - a. Male or female patients with a confirmed diagnosis of MS by McDonald criteria (18).
 - b. Age \geq 18 years.

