The following events are considered protocol-defined AEs and should be recorded on the AE log:

1. Weight gain: 5% increase compared to baseline
2. Increased blood pressure: increase of >20mm systolic or 10mm diastolic compared to baseline
3. Increased A1c: absolute increase of 1% or greater from baseline (Screening visit value) that is sustained across 2 consecutive measures
4. Hypokalemia: any potassium value below the lower limit of normal
5. New Osteopenia (compared to Baseline): DEXA T score between -1 and -2.5
6. Osteoporosis: DEXA T score less than -2.5
7. A DEXA T score drop of ≥ -0.5 during the study

As is typical, the study will not be powered based on safety and tolerability measures because AEs are anticipated to be rare and because the type and severity of AEs may be unpredictable. **The main secondary endpoint for safety and tolerability will be a comparison of the number of serious adverse events (SAE) over the study period in the ACTH group versus the placebo group.** A SAE will be considered any event with a score equal or greater than 3 on the Common Terminology Criteria for Adverse Events (CTCAE) version 4.03. AEs receiving a mild or moderate grade will also be compared between the two treatment groups.

C. Cognition

Cognitive dysfunction is ubiquitous in MS, affecting an estimated 40-70% of patients (33), and is a major cause of disruption in daily and occupational function in MS patients (34). The most common domains of cognitive impairment in MS are memory, processing speed, visuospatial functions, verbal abilities, sustained attention and

executive function (35). The BRB-N is a set of five cognitive tests developed by National MS Society's Cognitive Function Study Group as a research tool to detect cognitive changes in MS patients and to evaluate the effect of treatment interventions on cognition (36). The five neuropsychological tests comprising the BRB-N were chosen for their ability to assess the cognitive domains most frequently impaired in MS in a practical time period (20-30 minutes). The BRB-N includes the Selective Reminding Test (SRT, a test of verbal learning and delayed recall), the 10/36 Spatial Recall Test (10/36, visuospatial learning and delayed recall), the Symbol Digit Modalities Test (SDMT, sustained attention and processing speed), the Paced Auditory Serial Addition Test (PASAT, sustained attention and processing speed) and Word List Generation task (WLG, verbal fluency).

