- iii. **(optional) RNFL scan (circle scan) using N-site software** – Standard settings for peripapillary RNFL with the Spectralis axonal protocol will be used: 12 degree (3.45 mm) circular scan manually centered on the optic disc, ART = 100, circle = 12°, 768 A-scans.

For each scan, minimum quality score is 20 (with a goal quality score of \geq 25). If a quality score of \geq 20 cannot be obtained, data from that scan will not be included for analysis. The individual centers/technicians obtaining the OCT will evaluate only for quality of the OCT scans (i.e., no

formal clinical interpretation of the OCT results will be performed. The image alignment eye-tracking system (TruTrack, Heidelberg Engineering, Germany) will be utilized throughout.

Data submitted from each OCT session will include printouts of all RNFL scans, plus electronic files (.e2e format) containing each of the 2 (or 3) scans.

If a study site does not have access to the Spectralis OCT system, a different spectral-domain high-resolution OCT system such as Cirrus HD-OCT (Zeiss) may be used as an alternative, with similar scans acquired (RNFL scan, macular volume/posterior pole).

Change in thickness of the temporal quadrant peripapillary RNFL over the course of the study will be a secondary study endpoint. Exploratory endpoints will include changes in macular volume and changes in other RNFL regions (e.g. superior, inferior, nasal, and global).

6. Statistical Issues and Data Analysis

A. Study Design

The study design is a randomized, double-blind, placebo-controlled, multi-center, phase II clinical trial.

B. Sample Size Calculation

The main objective of the study is to investigate the safety and tolerability of pulsed ACTH in progressive MS patients over three years. The primary efficacy endpoint of the study is the proportion of subjects exhibiting a 20% increase (worsening) from baseline in the T25FW. No baseline data are available regarding the rate at which a pooled population of progressive MS (i.e., SPMS, PPMS and/or PRMS) patients experience 20% increase in T25FW. However, Bosma et al. (53) evaluated change over 2 years in all three components of the MSFC (T25FW, 9HP, and PASAT) in 191 PPMS patients, and found that 45% of patients showed a 20% or greater increase in T25FW. This data was used as the basis for sample size considerations, with the following assumptions:

The findings in PPMS patients (53)

1. will generalize to a mixed sample of any progressive MS phenotype.

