The possibility of mid-study therapy regimen change for some subjects (see Exclusion criteria g. and h.) will be accounted for in analysis by running models with and without these subjects to explore the impact of these changes on analysis results. If results from the two models are consistent, all subjects will be included in the final model.

There are multiple distinct outcomes of interest in this study; since each outcome measures a unique aspect of MS progression no adjustment for multiple comparisons is planned.

Primary endpoint:

Between group differences in the odds of a 20% or greater increase in T25FW, the primary outcome measure of clinical progression of MS, will be tested at 36 months using multiple logistic regression models adjusted for covariates. Generalized

estimating equation (GEE) models will be used to test for between group differences in change over time in clinical progression (20% or greater increase in T25FW) adjusted for covariates. To test for between group differences in time to clinical progression distribution curves, Cox proportional hazards models (conditional on model assumptions being met) or Kaplan-Meier analysis will be used.

Secondary endpoints:

Safety and tolerability

To evaluate safety and tolerability of ACTH, lists and descriptive statistics of adverse events, serious adverse event, and treatment compliance will be compiled and calculated for each group at each visit. Fisher's exact tests will be used to test for between group differences in specific adverse event rates, serious adverse event rates, and treatment compliance rates.

Between group differences in mean changes in physical exam and laboratory measures (weight, blood pressure, HgbA1c, bone mineral density) will be tested using two-sample t-tests. In addition, between group differences in the proportion of subjects with abnormal blood pressure, HgbA1C, electrolyte and bone mineral density levels will be tested using Chi-square tests or Fisher's exact tests.

Change in ambulation, cognition, and global measures of MS-related disability scores

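### Hypothesis 1 claims that pulsed ACTH is safe, but the planned safety inference consists only of tests for a difference, with no interval to bound the excess risk

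*Combined protocol and SAP*

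**What the plan says.** Section 3, item 1, predicts that monthly pulsed ACTH "will be safe and well-tolerated in progressive MS patients". No acceptable level of excess harm goes with the prediction. Section 6.B opens: "The main objective of the study is to investigate the safety and tolerability of pulsed ACTH in progressive MS patients over three years".

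Section 5.B makes the comparison of SAEs between arms the leading safety endpoint and defines the term: "A SAE will be considered any event with a score equal or greater than 3" on CTCAE version 4.03. The same section says that "the study will not be powered based on safety and tolerability measures", on the ground that adverse events are expected to be uncommon and hard to predict.

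Section 6.E provides for lists and descriptive statistics of adverse events by group and visit. It then sets out the inference. Fisher's "exact tests will be used to test for between group differences in specific adverse event rates", and the same test is named for SAE and compliance rates. Mean changes in weight, blood pressure, HgbA1c and bone mineral density "will be tested using two-sample t-tests". Proportions with abnormal values get chi-square or Fisher tests. The plan gives no confidence interval, no margin and no rule for judging Hypothesis 1, and it does not say how a non-significant safety test will be interpreted.

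**The concern.** Hypothesis 1 claims that important harm is absent. A test of no difference can contradict that claim but cannot support it, because a large p-value is also what a small trial produces when harm is present but undetected. The plan therefore has no inferential route to its own first hypothesis. The trial could finish with a clinically large excess of SAEs on ACTH, a p-value well above 0.05, and no planned statement of how large an excess the data still allow. That statement is what a reader of a safety-led phase II trial needs.

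**Working it through.** **Inputs from the documents.** 100 subjects randomized 1:1, so 50 per arm; dropout of up to 10-20%, so as few as 50 × 0.80 = 40 per arm (section 6.B). Two-sided alpha of 0.05 is stated for the primary endpoint (section 6.B).

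**Assumptions.** The same alpha and sidedness apply to the safety tests. The unit is a subject with at least one SAE. Section 5.B speaks of the number of SAEs, but a Fisher test compares proportions of subjects. The documents give no placebo SAE risk, so a range is used.

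**The plan's own figure.** For 0.6 versus 0.3 with pooled variance:

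n = [1.960 × √(2 × 0.45 × 0.55) + 0.842 × √(0.6 × 0.4 + 0.3 × 0.7)]² / 0.3² = 41.97, so 42 per arm.

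This matches section 6.B. The weakness for safety does not come from an error in the sample size.

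**Power for a doubled SAE risk.** Exact power is the sum, over all pairs of counts with two-sided Fisher p ≤ 0.05, of the product of the two binomial probabilities.

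| Placebo to ACTH risk (assumed) | 50 per arm | 40 per arm |
|---|---|---|
| 5% to 10% | 6.3% | 4.3% |
| 10% to 20% | 19.5% | 16.2% |
| 15% to 30% | 35.4% | 28.1% |
| 20% to 40% | 51.5% | 40.8% |
| 25% to 50% | 67.5% | 55.9% |
| 30% to 60% | 82.9% | 72.5% |

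Power passes 50% at a placebo risk of about 19.6% with 50 per arm and about 23.3% with 40 per arm.

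**What the test needs, 50 per arm.** 5 v 0 gives p = 0.056; 6 v 0 gives p = 0.027. With 5/50 on placebo, 13/50 on ACTH gives p = 0.066 and 14/50 gives p = 0.040, so significance needs an observed ratio of 14/5 = 2.8.

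**What an interval would show.** The Newcombe interval is built from the Wilson score limits of each proportion, which are 0.112 to 0.330 for 10/50 and 0.043 to 0.214 for 5/50.

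- 10/50 v 5/50 (Fisher p = 0.26), difference 0.10:
  - lower limit = 0.10 − √[(0.200 − 0.112)² + (0.214 − 0.100)²] = −0.043
  - upper limit = 0.10 + √[(0.330 − 0.200)² + (0.100 − 0.043)²] = +0.242
- 5/50 v 5/50 (p = 1.0), difference 0: limits ±√[(0.214 − 0.100)² + (0.100 − 0.043)²] = ±0.127. The risk ratio is 1.0 (95% CI 0.31 to 3.24), so equal observed counts would not exclude a tripling.

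**Could a formal non-inferiority test replace the difference tests?** Assume a 10-point margin, one-sided alpha 0.025, 80% power and equal true risks p. Then n = (1.960 + 0.842)² × 2p(1 − p) / 0.10², which is 75, 142 or 252 per arm for p = 5%, 10% or 20%. All exceed 50, so estimation is what this sample size can support.

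**The case against.** The strongest reply is that the protocol is open about this. Section 5.B says that safety is not powered, section 6.E provides descriptive tables for each group, and section 7.G has an unblinded board review safety at 6 and 12 months and then annually, with a detailed analysis of all adverse events after the first year. These points stand, and they narrow the concern. Group percentages are planned, so the point difference can be read off and only its uncertainty is missing. Board review protects participants during the trial, but it is discretionary, with no pre-specified stopping rules, and it does not supply the final inference. Disclosing low power does not bound the excess risk either.

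A reader might infer that the sponsor intends to report non-significance as proof of safety. The documents do not support that: no section says how a non-significant safety result will be read. The misreading is possible, not planned.

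A reader might also infer that a doubling of SAE risk would be missed whatever the background rate. That is not so. At 25% to 50% the power is about 67% with 50 per arm. Because an SAE here is any grade 3 or higher event over three years, a placebo risk of that size cannot be excluded, although the protocol's expectation of uncommon events points lower.

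Finally, the figures above concern SAEs. The t-tests are less weak: with 50 or 40 per arm they have 80% power for a mean difference of about 0.57 or 0.63 SD. Protocol-defined events such as 5% weight gain may also be more frequent than SAEs.

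**Conclusion.** The concern holds in a limited form. Whatever the event rate, a non-significant difference test cannot support Hypothesis 1, and the plan offers no other inference for its stated main objective. The size of the problem depends on a placebo SAE risk that the documents do not give. Below roughly 20-23% a true doubling would usually go undetected; above that it would more often be detected than not. These figures assume two-sided testing at 0.05 and count subjects with at least one SAE. The gap is the missing interval and the missing statement on interpretation. It is neither an error in the sample size nor a failure to admit limited safety power. It should be corrected, because the remedy is cheap and the objective is the trial's main one.

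**What to change.** In section 6.E, under safety and tolerability:

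- Make the main analysis the risk difference, ACTH minus placebo, with a 95% score-based interval. Apply it to subjects with at least one SAE, each adverse event of concern named in section 5.B, and each protocol-defined adverse event already collected.
- Give 95% confidence intervals for the mean differences now assessed by t-test.
- State that Hypothesis 1 is addressed by estimation. Report the upper limit as the bound on excess risk: only excesses above it are ruled out.
- State that p > 0.05 will not be described as evidence of safety.
- Keep the Fisher tests as flags only. Fisher's test is conservative and can disagree with a score interval near the threshold; the interval should govern.

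This sets no acceptable excess, so it yields an estimate and not a pass or fail verdict on Hypothesis 1. That fits what 50 per arm can deliver. The cost is SAP wording, with no new data, visits or subjects. The downside is that the safety conclusion will read less favourably.

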Between group differences in study endpoint mean of each of the secondary outcomes: change in ambulation (6MWT, MSWS-12, Hauser Ambulation Index), change in cognition (eight subtests of the five BRB-N tests), and change in MSFC z-scores will be tested using multiple linear regression models adjusted for baseline score and other covariates. Mixed model analysis of repeated measures, utilizing data collected at all time points, will be used to test for between group differences in change over time in mean secondary outcome measures adjusted for covariates. Between group differences in the odds of EDSS progression will be tested using multiple logistic regression models adjusted for other covariates. Generalized estimating equation (GEE) models will be used to test for between group differences in change over time in progression rates adjusted for other covariates. Cox proportional hazards models (conditional on model assumptions being met) or Kaplan-Meier analysis will be used to test for between group differences in time to EDSS progression.

OCT Temporal Quadrant RNFL

OCT temporal quadrant RNFL measurements from one eye per subject will be used for analysis purposes; randomly selected unless the patient has a history of optic neuritis in which case the unaffected eye will be selected. Between group differences in change in OCT temporal quadrant RNFL thickness will be tested using a multiple linear regression model adjusted for baseline thickness and other covariates. Multiple linear regression models will also be used to test for between group differences in three year rate of change adjusted for other covariates. Separate mixed model analyses of repeated

measures will be used to test for between group differences in 1) change over time in RNFL thickness and 2) change over the 3 years in annualized rates of RNFL change.

Exploratory endpoints

Fatigue

Between group differences in study endpoint mean FSS will be tested using a multiple linear regression model adjusted for baseline FSS score and other covariates. Mixed model analysis of repeated measures, utilizing data collected at all time points, will be used to test for between group differences in change over time in mean FSS adjusted for covariates.

Other vision measures

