Multiple linear regression models will be used to test for between group differences in LCVA scores adjusted for other covariates. Binocular LCVA scores will be used to test for a treatment effect on vision changes; monocular LCVA scores will be used for correlation with OCT measures (from the matching eye). Generalized estimating equation (GEE) models will be used to test for between group differences in change over time in vision loss rates adjusted for other covariates. In addition correlation of LCVA with OCT measures (RNFL and macular volume) will be evaluated using Pearson correlation analysis (Spearman correlation will be used if measures have skewed distributions).

Between group differences in mean OCT macular volume scan measures will be tested using multiple linear regression models adjusted for covariates. mixed model analyses of repeated measures will be used to test for between group differences in change over time in OCT macular volume measures.

7. Study Procedures

A. Schedule of study procedures:

1. Symptoms questionnaire for subjective adverse events at baseline, 3, 6 and 12 months and then annually.
2. Comprehensive metabolic panel (CMP) and hemoglobin A1C (HbgA1C) at screening, 6 and 12 months, and then annually.
3. EDSS and DEXA scan (both hips/femurs and lumbar spine) at screening and then annually.
4. OCT at baseline and then annually.
5. MSFC, T25FW, 6MWT, LCVA, MSWS-12, AI, FSS and BRB-N at baseline and then annually.
6. Practice sessions (at screening visit:
 - a. BRB-N - 1 practice session

- b. PASAT - 2 practice sessions (in addition to the one administered during BRB-N)
- c. 9HP - 3 practice sessions

Table 1. Study Schedule

	V1 Screen 0 to -4 wks	V2 Baseline M0	V3 *** M3	V4 M6	V5 M12	V6 M18	V7 M24	V8 M30	V9 M36
Informed Consent	X								
Inclusion/Exclusion	X								
Injection Training		X							
Blood Pressure		X	X	X	X	X	X	X	X
Weight		X	X	X	X	X	X	X	X
Safety Lab Tests^a	X			X	X		X		X
Skin & Edema Assessment		X	X	X	X	X	X	X	X
OCT		X			X		X		X
LCVA		X			X		X		X
EDSS	X				X		X		X
Timed 25-Ft Walk		X			X		X		X
9-Hole Peg Test	XXX	X			X		X		X
PASAT (apart from BRB-N)	XX								
6 Minute Walk Test		X			X		X		X
MS Walking Scale - 12		X			X		X		X
Fatigue Severity Scale (FSS)		X			X		X		X
Hauser Ambulation Index		X			X		X		X
Brief Repeatable Battery	X	X			X		X		X
DEXA Scan^b	X ^c				X		X		X
Randomization		X							
Symptom Questionnaire		X	X	X	X	X	X	X	X
Concomitant Medications		X	X	X	X	X	X	X	X

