Subjects will be asked to contact their study site if they develop new symptoms that are concerning to them. The local study coordinator will record the reported symptoms on the Unsolicited AE Form, which will be reviewed by the local investigator. An unscheduled study visit will occur if the local investigator deems these AEs as potentially serious, possibly related to study medication, and/or requiring in-person assessment. If the reported symptoms are interpreted as mild and/or unrelated to study medication, the subject may be referred to their primary physician or advised to report back by phone with updates about symptom

evolution/resolution. Unscheduled visits will not be routinely performed for suspected MS relapse (see section 7D, Relapses), although they may occur in this situation if the reported symptoms are interpreted as a possible treatment-related AE. Assessments/procedures performed at an unscheduled visit will include all of the assessments done at Visit 3 (see Table 1) with the exception of study drug distribution; any further assessments and/or procedures (e.g. physical examination, other tests, referrals) will be done at the discretion of the local investigator.

F. Early Termination and Intent to Treat

Once subjects are randomized, regardless of if or the length of time they have been on blinded treatment, they will be included in the efficacy (intent to treat) analysis if efficacy data are available (that is, if they have completed at least one annual follow-up visit). Subjects who withdraw (e.g., due to side effects) prior to completing the Month 12 visit will be asked to return the study drug to the site, and to participate in annual phone calls (Months 12 and 24), and to return to the site for the final visit at Month 36. Subjects who withdraw after completing the Month 12 visit will be asked to return the study drug to the site, and to complete the remaining annual study visits (i.e., Month 24 and Month 36) even though they are not receiving drug. Subjects are of course allowed to decline further participation, in which case they would be considered lost-to-follow-up.

G. Data Safety Monitoring

A DSMB will be formed and will consist of one MS specialist, one neurologist familiar with the evaluation and treatment of MS but not otherwise associated with the study, and the study biostatistician. A DSMB chairperson will be chosen from one of the two neurologists on the DMSB.

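### Mean changes in weight, blood pressure, HbA1c and bone density are compared by unadjusted t-tests at no named visit, although a baseline-adjusted repeated-measures model could use the readings already scheduled

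*Combined protocol and SAP*

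**What the plan says.** Section 6.E, under Safety and tolerability, tests mean changes in exam and laboratory measures as follows: "weight, blood pressure, HgbA1c, bone mineral density) will be tested using two-sample t-tests". It does not say at which visit, whether baseline is adjusted for, or what happens when a reading is missing. The same paragraph adds a categorical analysis: "between group differences in the proportion of subjects with abnormal blood pressure, HgbA1C, electrolyte and bone mineral density levels will be tested using" Chi-square or Fisher's exact tests. Weight is not in that list. The by-visit summaries ("will be compiled and calculated for each group at each visit") cover adverse events, serious adverse events and compliance, not these four measures.

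For ambulation, cognition and MSFC scores, Section 6.E plans regression adjusted for the baseline score and, in addition, "Mixed model analysis of repeated measures, utilizing data collected at all time points". Similar models are written for RNFL thickness, fatigue and macular volume. None is written for the safety measures.

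Table 1 (Section 7.A) schedules weight and blood pressure at baseline and at Months 3, 6, 12, 18, 24, 30 and 36, and DEXA at screening and at Months 12, 24 and 36. The laboratory schedule is "Comprehensive metabolic panel (CMP) and hemoglobin A1C (HbgA1C) at screening, 6 and 12 months, and then annually", that is, Months 6, 12, 24 and 36 after screening. The Month 3 visit may be held by phone.

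Section 7.F deals with "Subjects who withdraw (e.g., due to side effects) prior to completing the Month 12 visit": they are asked to take phone calls at Months 12 and 24 and to attend in person at Month 36. Those who withdraw later are asked to attend the remaining annual visits off drug. Only those who decline become lost to follow-up.

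**The concern.** Section 6.B makes safety and tolerability over three years the main objective. Yet the continuous safety measures, which are those most directly tied to steroid-type effects, get a simpler analysis than the efficacy scores.

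Three things follow. First, a change-score t-test at one visit makes no use of the other readings and adjusts for baseline less efficiently than a regression would. Second, it drops every subject without a reading at that visit, even when earlier on-drug readings are on file. If leaving is related to the size of the change, the comparison can understate harm. Third, the choice of visit is open. Weight could be tested at any of seven visits, Section 6.E plans no multiplicity adjustment, and Section 6.D leaves the study statistician unblinded. The choice is better fixed in advance.

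**Working it through.** **The plan's own figure.** The documents give no sample size, SD or target difference for these measures; Section 5.B says the study is not powered on safety. The only stated size is for the walking endpoint, and it reproduces: [1.96·√(2·0.45·0.55) + 0.84·√(0.6·0.4 + 0.3·0.7)]² / 0.3² ≈ 42 per arm.

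**Inputs from the documents.** 50 per arm; dropout of up to 10-20% (Section 6.B); the visit counts above.

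**Inputs assumed.** Between-visit correlation *r* of 0.5 to 0.9, the same for every pair of visits, and equal variance at each visit.

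**What the t-test can detect** (80% power, two-sided 0.05), in SDs of change: 2.80·√(2/n). This gives 0.56 with 50 per arm, 0.59 with 45 and 0.63 with 40.

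**Precision, Month 36 contrast, complete data.** The variance of a change score is proportional to 2(1 − r); of a baseline-adjusted value, to 1 − r². The ratio is (1 − r²)/[2(1 − r)] = (1 + r)/2, which is 0.75 at r = 0.5 and 0.95 at r = 0.9. All of this gain comes from baseline adjustment, none from the intermediate visits.

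**Precision, difference averaged over k visits.** The ratio to a one-visit change t-test is [(1 + (k − 1)r)/k − r²]/[2(1 − r)].
- k = 7, r = 0.5: (0.571 − 0.25)/1 = 0.32.
- k = 7, r = 0.9: (0.914 − 0.81)/0.2 = 0.52.
- k = 6 (Month 3 by phone): 0.33 and 0.53.

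**Missing readings.** This was simulated with 50 per arm, readings at baseline and Months 12, 24 and 36, and a true Month 36 difference of 0.50 baseline SD building up linearly. Half the leavers go after Month 12 and half after Month 24. In the ACTH arm, those with the largest observed change leave; in the placebo arm, leaving is random. There were 400 runs per row, with a simulation error of about 0.01. Entries are mean estimated differences.

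| r | Dropout ACTH / placebo | t-test, none return | t-test, half return | t-test, all return | Repeated measures, none return |
|---|---|---|---|---|---|
| 0.5 | 10% / 10% | 0.407 | 0.444 | 0.497 | 0.507 |
| 0.5 | 20% / 10% | 0.314 | 0.429 | 0.485 | 0.491 |
| 0.5 | 20% / 20% | 0.323 | 0.415 | 0.492 | 0.504 |
| 0.8 | 10% / 10% | 0.445 | 0.470 | 0.502 | 0.508 |
| 0.8 | 20% / 10% | 0.379 | 0.448 | 0.501 | 0.491 |
| 0.8 | 20% / 20% | 0.384 | 0.434 | 0.503 | 0.499 |

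Returners are assumed to keep the effect off drug. The repeated-measures estimate here is a likelihood estimate of change without baseline adjustment, so the last column shows bias, not precision. It is close to 0.50 because dropout was made to depend only on observed readings.

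**The case against.** A change-score t-test is valid under randomisation, and safety is explicitly unpowered. Because no visit is named, t-tests at every visit are also a possible reading, so the plan does not strictly discard the repeated visits. These points stand. They make this a matter of efficiency and specification, not an invalid test. Even visit-by-visit t-tests would omit subjects without a reading at each visit.

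A reader might go further and infer that the plan loses the subjects who leave because of side effects, so that the comparison is biased toward no harm. The documents do not support that. Section 7.F asks those subjects back at Month 36, and also at Month 24 if they leave after Month 12. Readings before withdrawal can also count elsewhere. Section 5.B logs threshold changes in weight, blood pressure, HbA1c and T-score as adverse events, Section 6.E tests specific adverse event rates and abnormal values, and the main safety endpoint is the serious adverse event comparison. Withdrawal may also follow insomnia or injection pain, which need not relate to these measures. Those other analyses dichotomise, however, and do not estimate mean change.

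A worst-case calculation is also tempting. If exactly the top 10% or 20% on final change left the ACTH arm and none returned, the ACTH mean would be understated by φ(z)/(1 − q) = 0.195 or 0.350 SD of change. That is an extreme bound, not an expectation.

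Finally, the 32-52% variance ratio should not be read across to all four measures. It holds only for a visit-averaged difference.

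**Conclusion.** The point holds as one of precision, specification and conditional bias. The four continuous safety measures are planned for unadjusted t-tests at an unstated visit, while better-suited models are already in the plan and the readings are already scheduled.

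The precision gain is modest for a Month 36 contrast (5-25% less variance) and large for visit-averaged blood pressure (about 48-68% less with seven readings). Both rest on the assumed correlations and equal variances.

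The size of any bias depends on how many subjects decline to return and why, which the documents cannot fix. With 20% ACTH dropout it runs from about 0.12-0.19 SD, if none return and the largest observed changes leave, to none if all return with the effect persisting. For returners a separate issue remains: Month 36 values are then off drug and may dilute an on-treatment effect, and the plan is silent on this.

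**What to change.** In Section 6.E, replace the t-tests with a repeated-measures mixed model over all scheduled post-baseline visits, with terms for baseline value, centre, visit, arm and arm-by-visit. The covariates that Section 6.E asks of its models would apply as well. State the estimate in advance: the Month 36 arm difference for weight, HbA1c and bone density, where effects may accumulate, and the visit-averaged difference for blood pressure, each with a 95% CI. Include all available values, including those after drug is stopped, and add an on-treatment summary alongside, because off-drug values alone could hide a reversible effect.

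The cost is SAP wording and a little programming; no new data are needed. Two limits should be written down. The model corrects only dropout explained by observed values, so a sensitivity analysis is worth adding. It also recovers no bone data for subjects who leave before Month 12 and do not return, since the first repeat DEXA is at Month 12.
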